
outcomes and data post-transplant will be compared between Arm 1 and Arm 2 where a) any study drug (G/P) related severe treatment emergent adverse events are included as a clinical outcome for Arm 1 and b) all events of treatment emergent Grade ≥ 3 laboratory values and severe G/P-related treatment emergent adverse events are included as clinical outcomes for Arm 1.
 
4) To compare time to deceased donor kidney transplantation among all patients who enrolled in this MYTHIC trial to transplant candidates from the Organ Procurement and Transplantation Network (OPTN) database; MYTHIC participants will be matched 1:3 to OPTN patients on demographics and characteristics known to influence waiting time including waiting list priority, blood group, geographic region, and sensitization.

Investigators: Multi-center, names on file with sponsor

Study Sites: Up to 7 sites

Study Population: HCV-negative subjects wait-listed for a kidney transplant

Number of Subjects to be Enrolled: Up to 90, including a target number of 30 kidney transplantation events from study eligible HCV RNA-positive kidney donors.

Methodology:
 
This is an open-label, multi-center, two-arm study to evaluate the efficacy and safety of fixed-dose combination tablets of glecaprevir/pibrentasvir (G/P) in HCV-negative subjects who consent to receive a kidney transplant from an HCV RNA-positive deceased kidney donor. 90 subjects will be consented for trial participation, out of whom 30 subjects at up to 7 sites are planned to receive an HCV RNA-positive kidney meeting study criteria and will be enrolled into a post-transplant treatment arm (Arm 1) receiving open-label G/P for 8 weeks post-transplant. The remaining enrolled subjects including those who do not receive a kidney meeting study criteria from an HCV RNA-positive donor will be followed in Arm 2 for the minimum duration of 1 year post-enrollment. Arm 2 includes subjects who do not receive a kidney at one of the study sites or who receive a standard of care kidney transplant (Arm 2B5 patients will be censored at the time of transplant at a non-study site). For subjects enrolled in Arm 1 of the study, the

first dose of G/P will be given as early as 3 days post-transplant. Patients must be out of the ICU, able to eat and drink, and take oral medications, so that G/P treatment can be safely initiated orally as judged by the site investigator.

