Eligible subjects will initiate G/P 300 mg/120 mg QD for 8 weeks early after kidney transplantation. Day 3 post-transplant is targeted for the start of G/P treatment for HCV RNA-positive kidney recipients, with the conditions met that the subject should be out of the ICU, able to eat and drink and take medications orally, and in the judgement of the investigator, starting oral G/P treatment is safe for the subject.

A delay in commencing G/P after day 3 should only take place because the responsible site investigator and/or responsible clinicians believe that G/P cannot be safely administered or because of a high probability that G/P will subsequently need to be discontinued or held for prolonged period because the patient is likely to experience clinical deterioration. In the case of any patient who has not started G/P by day 3 after transplantation, the site investigator will discuss that case with the Principal Investigator [name], or delegate, and develop and document a plan to start G/P at a later time.

Post Treatment (PT) Period for recipients of HCV RNA-positive kidneys in Arm 1:

Subjects who complete or prematurely discontinue G/P treatment will be followed for 24 weeks after their last dose of study drug to evaluate efficacy and to monitor HCV RNA and the emergence and persistence of viral substitutions in the NS3 and NS5A, and subjects will be followed up at 1 year post the date of kidney transplant to assess graft function and survival and anti-HCV antibody serology.

Figure 1A: Overall Study Schematic

[figure not shown]
Treatment and PT Period for Study Arm 2A recipients of HCV RNA-negative/HCV antibody-positive kidneys:

Eligible subjects will be followed for 24 weeks after transplantation or 12 months after enrollment, whichever is longer, with surveillance for HCV infection using HCV RNA testing on week 1, week 4 (usual care), and week 24 (Figure 1B) after transplantation. A maximum number of up to n=20 subjects who are enrolled into the study can accept a study-eligible kidney from an HCV RNA-negative/HCV antibody-positive donor and be assigned to Arm 2A and will be followed in the study for 24 weeks post-transplant. The last study-eligible kidney transplant from an HCV RNA-negative/HCV antibody-positive donor in Arm 2A must occur no later than 24 weeks after the date of the 30th kidney transplant from an HCV RNA-positive donor in Arm 1 (see also section 5.1.5).

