Subjects who prematurely discontinue treatment during the transplantation phase should return for a Treatment Discontinuation Visit and undergo the study procedures as outlined in Tables [5](#) and [6](#).

In Arm 1, 30 candidates will undergo kidney transplantation with kidneys from HCV RNA-positive donors. After n=30 kidney transplantation events from HCV RNA-positive donors have occurred, no further subjects will be enrolled into the study. Already enrolled subjects who receive an HCV RNA-positive donor kidney offer that meets study criteria and are scheduled to be transplanted within 24 hours after the 30th kidney transplant from an HCV RNA-positive donor will also be allowed into treatment arm A of the study.

Patients enrolled in the trial will be notified by phone that the HCV RNA-positive arm of the trial has completed enrollment and remaining subjects (now in Arm 2) will have the ability to accept (i) a study-eligible kidney from an HCV RNA-negative/HCV Ab-positive donor up until 24 weeks after the last kidney transplant event from a study-eligible HCV RNA-positive donor, (ii) a standard of care kidney transplant, or remain on the waiting list for the duration of the study. G/P treatment, if needed, will be provided free of charge to a subject in Arm 2A who developed HCV viremia after up to 24 weeks post-transplant of a kidney from an HCV RNA-negative/HCV Ab-positive donor.

5.1.5.1 G/P treatment phase/Visits and laboratory evaluations after transplantation for subjects who receive a study eligible HCV RNA-positive kidney in Arm 1

Visit 1: Peri-transplant visit

The treating physician will evaluate the patient's overall condition and make a judgment on whether transplantation is safe. The following recipient-donor-kidney match results exclude transplantation in this protocol: a) Blood group incompatibility between donor and recipient; b) Cross match reactivity, or clinically meaningful donor specific antibody, or other immunological reactivity related to an allograft offer deemed a substantial risk for rejection by the responsible investigator.

The following research procedures and activities will be performed:

- Obtain medication data
- Donor blood sample (if available)
- Assessment of recipient and donor-kidney match for exclusion from transplantation in this protocol

Visit 2: Post-kidney transplant (Day 3 ± 1 day)

The study staff will meet the subject in their hospital room, three days after their kidney transplant.

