8.1 Statistical and Analytical Plans

The data analysis will be generated using SAS version 9.4 or higher for windows and/or STATA software version 14.0 or higher (StataCorp LP, College Station, TX). SAS Institute Inc. SAS and all other SAS Institute Inc. product or service names are registered trademarks or trademarks of SAS Institute Inc., Cary, NC, USA. All statistical tests (if applicable) and confidence intervals will be two-sided with an alpha level of 0.05.

Descriptive statistics will be provided, such as the number of observations (N), mean, and standard deviation (SD) for continuous variables and counts and percentages for discrete variables.

The efficacy and safety of the “reactive” G/P treatment of patients who become HCV RNA-positive after receiving a kidney from a study eligible HCV RNA-negative/HCV Ab-positive donor in Arm 2A are not an objective of this study, and they are not included in assessments of efficacy or safety described below. The time to transplant and clinical outcomes and data post-transplant from patients in Arm 2A are included in those secondary endpoints.

The primary analysis will occur after all recipients of HCV RNA-positive kidneys in Arm 1 have completed post-treatment week 12 visit (corresponding to SVR₁₂ data collection) or prematurely discontinued study. The primary analysis of SVR₁₂ will be performed on the intention-to-treat (ITT) population defined as all enrolled subjects who received a study eligible HCV RNA-positive kidney and received at least one dose of G/P according to actual treatment received (Arm 1).

No data will be imputed for any efficacy or safety analysis except for analyses of SVR endpoints (HCV RNA data). HCV RNA values will be selected for the analyses of all SVR endpoints (e.g., SVR₄ and SVR₁₂, SVR₂₄) based on defined visit windows. A backward imputation method will be used to impute missing responses for SVR analyses. Additional details of analyses to be performed will be specified in the Statistical Analysis Plan.

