Summary of Statistical Analysis Plan for MYTHIC Study

[Draft: April 26, 2020]

Part	Patient Group(s)	Outcome	Statistical Analysis ^a
1	Arm 1 (ITT)	SVR12	- estimated probability of SVR12 and 95% confidence interval (CI) - exact binomial calculations
2	Arm 1 (ITT)	Virologic failure (VF)	- estimated probability of SVR12 and 95% confidence interval (CI) - exact binomial calculations
3	Arm 1 (ITT)	Post-treatment virologic relapse	- estimated probability of SVR12 and 95% confidence interval (CI) - exact binomial calculations
4	All patients	HCV-viremic kidney transplant (KT); i.e., Arm 1 KT	- cumulative incidence and 95% CI - death and other KT types treated as competing risk - estimate non-parametrically, using Lin (1997) which proceeds through the cause-specific hazards, or Fan (2013) which uses Inverse Probability of Censoring Weighting (IPCW).
5	All patients	Non-HCV-viremic KT; i.e., Arm 2A-2B KT	- same as for component (4).
6	All, by Arm	Hospital admissions	- Arm treated as a time-dependent treatment - crude hospitalization rate per 100 patient-years (PY) and 95% CI - use robust variance estimator, to account for correlation among hospital admissions within-patient
7	All, by Arm	Hospital admissions	- Arm treated as a time-dependent treatment - proportional rates model (Lin et al., 2000) - robust SEs, to account for clustering within-patient
8(a)	All, and SRTR* controls	Kidney transplant	- exclude, from SRTR, all patients who indicated consent to receive an HCV-viremic KT (hereafter: SRTR*) - estimate prognostic score using SRTR* patients: KT as event - 1:5 matching (MYTHIC : SRTR*) based on prognostic score with caliper - Cox regression, with MYTHIC as lone covariate, stratified by matched set

8(b)	All, and SRTR* controls	Kidney transplant	Same as 9(a), but using exact matching on small set of predictors, with prognostic score used to break ties among potential matches
9	Arm 1 – ITT	Compliance	Treated as repeated binary (0/1) data, with 1 indicating compliance (i.e., having taken 80-120% of prescribed pills)
10	Arm 1 – ITT	Death	Time to event; Cox regression
11	Arm 1 – ITT	Graft failure	Time to event; Cox regression
12	Arm 1	Delayed graft function	DGF: binary (0/1) response. Compute OBS/EXP, where OBS=observed number of DGFs for Arm 1 and EXP= expected count based on logistic regression model fitted to HCV-negative UNOS patients from large academic centers

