13	Arm 1	Acute allograft rejection	AAR: Binary (0/1) response. Compute OBS/EXP, where OBS=observed number of AARs for Arm 1 and EXP= expected cunt based on logistic regression model fitted to HCV-negative UNOS patients from large academic centers
14	Arm 1	ALT elevation	Binary (0/1), with '1' corresponding to peak ALT > 5 x ULN, where ULN=upper limit of 'normal'.
15	All, by arm	Serious Adverse Event	SAE: recurrent event Arm treated as a time-dependent factor Proportional rates model, robust SEs to account for within-patient clustering
16	Arm 1, 2AB	eGFR	Repeated continuous response Linear mixed model, to account for clustering by patient
17	Arm 1, 2AB	Proteinuria	Binary response; logistic regression
18	Arm 1, 2AB	BK virus	Binary response; logistic regression

Notes:

a) Each of the above-listed analyses will be accompanied by appropriate summary statistics (e.g., mean, median, IQR, etc).

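### SAP Parts 6, 7 and 15 name a robust variance but no small-sample correction, so with about 30 patients in Arm 1 and at most 20 in Arm 2A the intervals are likely to be modestly too narrow

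*SAP*

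**What the plan says.** The SAP is a two-page table headed as a summary and marked as a draft. Part 6 asks for a crude hospitalization rate per 100 patient-years with a 95% confidence interval, and says to "use robust variance estimator, to account for correlation among hospital admissions within-patient". Part 7 fits a proportional rates model to the same events with "robust SEs, to account for clustering within-patient". Part 15 does the same for serious adverse events: "Proportional rates model, robust SEs to account for within-patient clustering". All three rows cover all patients by arm. For Parts 6 and 7 the coding is "Arm treated as a time-dependent treatment", and Part 15 says the same in nearly the same words. No row gives a finite-sample correction, a t or normal reference, or a scale for the limits, and no row lists the arm levels or the reference group.

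The protocol supplies the sizes. Enrollment is "Up to 90, including a target number of 30 kidney transplantation events" (Synopsis). Section 5.1.5 says "In Arm 1, 30 candidates will undergo kidney transplantation", and section 5.1.3 also admits transplants scheduled within 24 hours of the 30th. For Arm 2A, section 5.1 sets a cap: "A maximum number of up to n=20 subjects who are enrolled into the study". The error standard is in section 8.1: "All statistical tests (if applicable) and confidence intervals will be two-sided with an alpha level of 0.05".

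**The concern.** The sandwich variance is justified by a large number of independent clusters, here patients. With a few dozen patients and skewed recurrent counts it tends to be too small. Normal limits add to the problem, because they ignore the uncertainty in the variance itself. An arm's crude rate in Part 6 uses only the patients who spent time in that arm, so for Arms 1 and 2A the relevant count is about 30 and at most 20, not 90.

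These rows describe the burden of hospitalization and serious adverse events by arm. Safety is part of the primary objective (Protocol section 4.1), so intervals that are too short would overstate how well harms are known. In an arm with no events every residual is zero, the robust variance is exactly zero, and Part 6 would print an interval of zero width.

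**Working it through.** The documents state no event count, power or error rate for Parts 6, 7 or 15, so there is no figure of the plan's own to reproduce. The benchmark is 95% coverage and 5% two-sided error.

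**Inputs from the documents.** Arm 1: 30 patients followed 1 year after transplant. Arm 2A: at most 20. Total: up to 90. The only event frequency given is readmission of about 40% within 30 days of transplant (Protocol section 9.4.1).

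**Assumptions.** 0.5 to 1.5 events per patient-year, and gamma between-patient variance v of 0.5 to 2 (also v = 0 for the crude rate). Follow-up is 1 year at n = 30, uniform on 0.46-1 year at n = 10 and 20, and uniform on 0.1-1 year at n = 90.

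**Step 1: crude rate (Part 6).** With N_i events in time T_i, r = ΣN_i / ΣT_i and robust variance = Σ(N_i − r·T_i)² / (ΣT_i)². There were 20,000 replicates per setting (Monte Carlo error about 0.2 points), and replicates with no events were set aside. The corrected columns multiply the variance by n/(n−1) and use t with n−1 degrees of freedom. Coverage (%) of nominal 95% limits, as the range over all settings:

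| Patients | Log, normal | Linear, normal | Log, corrected | Linear, corrected |
|---|---|---|---|---|
| 90 | 93.3-94.8 | 91.8-94.1 | 93.8-95.2 | 92.2-94.5 |
| 30 | 91.5-94.0 | 89.2-93.0 | 93.2-95.9 | 90.2-94.4 |
| 20 | 91.0-94.9 | 86.6-92.0 | 93.6-97.3 | 88.6-94.1 |
| 10 (hypothetical) | 88.0-95.0 | 81.3-88.9 | 92.6-97.9 | 85.6-93.6 |

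The scale matters as much as the correction: on the linear scale the corrected limits still fall short.

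**Step 2: proportional rates model (Parts 7 and 15).** Arm was time-dependent (Arms 1, 2A and 2B after transplant against waitlist time), with sandwich errors from per-patient score residuals and a Wald test with no true arm effect. There were 36 scenarios with 63 to 90 patients in total, 30 in Arm 1 and 10 or 20 in Arm 2A, and 2,500 replicates each (Monte Carlo error about 0.4-0.6 points). Fits that did not converge, mostly arms with no events, were excluded (up to 12% at 0.5 per patient-year). Rejection at nominal 5%:

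| Contrast | Uncorrected, normal | n/(n−1) and t |
|---|---|---|
| Arm 1, 30 patients | 5.6-8.2% | 4.1-6.6% |
| Arm 2A, 20 patients | 4.8-8.2% | 3.0-6.0% |
| Arm 2A, 10 patients | 4.3-10.1% | 1.6-4.9% |

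For Arm 1 the mean robust standard error was 0.89-0.97 of the true standard deviation. At 1 or more events per patient-year every Arm 1 and Arm 2A figure was above 5%; at 0.5, several Arm 2A figures were at or below 5%. Model-based errors that ignore clustering rejected up to 28% for Arm 1.

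A smaller run of this model (about 500 replicates per setting) gave 8-11% uncorrected for Arm 1 and 4-8% with a patient-level jackknife and t limits. Its Monte Carlo error is about √(0.08 × 0.92 / 500) = 1.2 points, so it supports the direction and does not refine the size.

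**Step 3: widening.** The ratio of corrected to normal limits is t × √(n/(n−1)) / 1.96. For n = 30: 2.045 × √(30/29) / 1.96 = 1.061. For n = 20: 2.093 × √(20/19) / 1.96 = 1.096.

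**Step 4: no events.** For n patients with 1 year each at rate λ, the chance of no events is (1 + λv)^(−n/v). With n = 5 and λ = 0.5 this is 1.25^(−10) = 10.7% at v = 0.5 and 2^(−2.5) = 17.7% at v = 2.

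**The case against.** The strongest reply is that the SAP is a summary-level draft. It requires the variance to respect clustering and is silent on the rest, so it rules out no correction. That stands: a reader might infer that the plan has chosen the uncorrected estimator, and the text does not say so. The supportable point is that the choice is left open and that the ordinary form falls short at these sizes. Parts 1 to 3 do name exact binomial calculations for Arm 1, so a small-sample method was specified there and not here.

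A second reply is that all 90 patients are clusters. That does not help the Part 6 rate for Arm 1 or 2A. The model check used 63 to 90 patients with time-dependent arm and still found the Arm 1 test above 5% in every scenario. It would help if arms are pooled: Parts 16 to 18 combine 2A and 2B, and a 90/30 split leaves about 60 patients in Arm 2 as a whole.

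A third reply is that little depends on these rows. No arm test is stated, section 8.1 allows tests only where applicable, section 8.2 calls the aim feasibility and preliminary data, and section 8.1.4 summarizes waitlist hospital days descriptively. This limits the consequence, although Part 6 does call for a 95% interval.

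A reader might also infer that the arm tests will generally exceed 5%, or that zero-width intervals are likely. The documents do not support either. Some Arm 2A results are at or below 5%, and arms of 10 or 5 patients have no source in the plan. If 40% are readmitted within 30 days and patients are independent, the chance that none is readmitted in that month is 0.6^5 = 7.8% for five patients and 0.6^10 = 0.6% for ten, before any longer follow-up.

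**Conclusion.** The concern holds as a modest, correctable weakness. With the ordinary sandwich and normal limits, the Part 6 interval at 20 to 30 patients falls short of 95% by up to about 4 points on the log scale and up to about 8 on the linear scale. The Arm 1 contrast in the proportional rates model rejects at about 6-8% instead of 5%. The Arm 2A contrast may or may not exceed 5%, and the shortfall becomes larger only if that arm ends well below its cap of 20. All of this depends on event rates and between-patient variation that the documents do not give. No confirmatory conclusion is at risk. The use of robust errors is sound and should be kept.

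**What to change.** In Parts 6, 7 and 15, specify a delete-one-patient jackknife or a bias-corrected (Mancl-DeRouen type) sandwich variance, with t limits whose degrees of freedom come from the number of patients in the arm, on the log-rate scale. State the arm levels and the reference group. For the crude rate, the log-scale jackknife with t limits covered 93.4-95.7% at 30 patients and 93.3-95.7% at 20, under 0.5-1.5 events per patient-year, v of 0.5-2 and 1 year per patient.

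For an arm with no events, report the count, the patient-years and an exact Poisson upper limit. At 97.5% this is −ln(0.025) = 3.69 divided by the patient-years. It assumes no variation between patients, so it should be labelled as a minimum.

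The cost is SAP wording and a software option; no new data are needed. Intervals widen by about 6% at 30 patients and 10% at 20. With about 10 patients or fewer the contrasts can become conservative (1.6-4.9% for the simple correction), which makes a difference in harms easier to miss, so an arm that small should be reported descriptively.

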8.1.4 Secondary Clinical Outcomes

Secondary clinical outcome analyses will be performed for subjects prior to kidney transplant in both Arms 1 and 2, and post kidney transplant for those who receive a kidney transplant in Arms 1 and 2. For details on safety reporting and periods of safety reporting see section 6.1.4.

The cumulative incidence function curves of time to kidney transplant will be created for each type of kidney transplant (Arms 1, 2A, 2B), and cumulative incidence and standard error (SE) will be calculated for each type of kidney transplant.

An exploratory analysis will create cumulative incidence function curves of time to kidney transplant for the subgroups of Arm 2B if sufficient subjects are enrolled in Arm 2B.

The number and percentage of subjects with clinical outcomes while on waitlist and after study consent (SAEs, delisting from waitlist, death) among subjects who receive an HCV RNA-positive kidney (Arm 1) and among those subjects who do not receive an HCV RNA-positive kidney (all Arm 2 subjects) overall and with breakdown by category of Arm 2 (2A, 2B, 2C). In addition, the total number of inpatient hospital days while on waitlist in those who did receive an HCV RNA-positive kidney (Arm 1) and total inpatient hospital days in those who did not (Arm 2) overall and with breakdown by category of Arm 2 will be summarized descriptively with mean, median, standard deviation (SD), minimum and maximum.

We will match MYTHIC trial participants 1:3 to comparators derived from the Organ Procurement and Transplantation Network database. Matching will be based on demographics and baseline characteristics known to influence waiting time, including waiting list priority, blood group, geographic region, and sensitization. A comparison of time to kidney transplantation between the kidney transplant candidates enrolled in the MYTHIC trial and OPTN comparators will be performed using a Cox proportional hazards model.

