8.2 Determination of Sample Size

This study is primarily designed to demonstrate feasibility and to generate preliminary data related to cure rates (defined as SVR₁₂) from treating donor-derived HCV infection post kidney transplantation using G/P. For this reason, the sample size was not determined with reference to power to detect differences between groups for the primary objective. The lower bound of a one-sided 95% confidence interval using the Wilson's score method, for various SVR₁₂ rates with a total sample size of 30 subjects are provided in Table 10.

Table 10: Estimated Lower Bound for 95% Confidence Interval for Cure Rate Based on Observed Number of Cures

Sample Size	No. of Observed Cures	Observed Cure Rate	Lower Bound for 95% CI of Cure (Wilson's Score)
30	30	100.0%	93.8%
30	29	96.7%	85.4%
30	28	93.3%	81.0%
30	27	90.0%	76.9%
30	26	86.7%	73.0%

As a secondary objective, we will compare time to kidney transplantation between the estimated 75 - 90 kidney transplant candidates enrolled in this trial with 225-270 matched kidney transplant candidates from the OPTN list (1:3 match). We estimate that at least 40

patients (44%) of 90 enrolled patients will undergo kidney transplantation versus 20% (or less) of comparators from OPTN list during an estimated 6 months of follow-up, with 80% power to detect a difference between groups.

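### SAP Part 8 gives no date for the consent that removes SRTR controls; applied as written, it selects controls on future information and, against a no-viremic-access comparator, pulls the hazard ratio toward the null

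*SAP*

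**What the plan says.** SAP Part 8(a) compares time to kidney transplant between MYTHIC participants and registry controls. Its first instruction is to "exclude, from SRTR, all patients who indicated consent to receive an HCV-viremic KT (hereafter: SRTR*)". The reduced pool is then used twice: to "estimate prognostic score using SRTR* patients: KT as event", and for "1:5 matching (MYTHIC : SRTR*) based on prognostic score with caliper". The model is "Cox regression, with MYTHIC as lone covariate, stratified by matched set". Part 8(b) keeps the same SRTR* controls and changes only the matching; it refers back to a Part 9(a), apparently meaning 8(a). Neither part states a time zero for controls, a date by which consent must have been recorded, or what happens to a control who consents during follow-up.

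The protocol describes a different comparator. Section 8.1.4 says: "We will match MYTHIC trial participants 1:3 to comparators derived from the Organ Procurement and Transplantation Network database". It continues: "Matching will be based on demographics and baseline characteristics known to influence waiting time, including waiting list priority, blood group, geographic region, and sensitization". There is no exclusion for consent to viremic kidneys. Section 8.2 sizes the comparison on the same 1:3 ratio and expects that at least 40 "patients (44%) of 90 enrolled patients will undergo kidney transplantation versus 20% (or less) of comparators from OPTN list", over an estimated 6 months, with 80% power.

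**The concern.** A registry candidate can consent to a viremic kidney only while still waiting. If consent at any time triggers exclusion, the rule deletes people who were eligible controls at the index date, had not been transplanted for some time, and then consented. A control transplanted early cannot be deleted this way. The deletion discards event-free control time, so the retained controls appear to be transplanted faster than the candidates they represent. MYTHIC participants are all retained from enrolment, so the selection acts on one side only. Because the prognostic score is estimated in the same pool, it carries the same selection into the matching.

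This is the only comparison for which the protocol states power, and it addresses secondary objective 4. What is at stake is the size of the reported gain in access to transplant.

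**Working it through.** **Inputs from the documents.** Protocol 8.2 gives 44% transplanted in MYTHIC and 20% in controls at 6 months, with 75 to 90 participants and 225 to 270 controls. Protocol 8.1 sets a two-sided alpha of 0.05.

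**The plan's own figure.** For 44% versus 20%, a two-proportion test has power 99.1% (90 vs 270) and 97.6% (75 vs 225). The event-based (Schoenfeld) formula gives 97.9% with 93.6 events and 95.5% with 78 events. The stated 80% is therefore right only as a lower bound. It contains no input for consent, so it does not bear on this point.

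**Hazards implied by 8.2.**
- Control: λ = −ln(0.80)/0.5 = 0.446 per year.
- Hazard ratio: ln(0.56)/ln(0.80) = 2.60.

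**Assumption.** The documents give no rate or timing of consent among registry candidates. I take a constant consent hazard g of 0.1, 0.2 or 0.4 per year, independent of the transplant hazard.

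**Model.** Let s = λ + g and let F be follow-up in years.
- Transplanted before any consent: K = (λ/s)(1 − e^(−sF))
- Neither by F: N = e^(−sF)
- Deleted as later consenters: D = 1 − K − N
- Retained person-time: P = λ[1 − e^(−sF)(1 + sF)]/s² + F·N
- Retained control rate: r = K/P. The overstatement is r/λ, and the estimated hazard ratio is 2.60 divided by that.

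The reference is the same controls censored at consent, whose rate is λ.

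**One case in full (F = 0.5, g = 0.4).** s = 0.846 and N = e^(−0.423) = 0.655. K = (0.446/0.846)(0.345) = 0.182. D = 1 − 0.182 − 0.655 = 0.163. P = 0.042 + 0.328 = 0.370. r = 0.182/0.370 = 0.492, and r/λ = 1.10. The hazard ratio is about 2.36.

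| F | g per year | deleted | r/λ | 2.60 becomes |
|---|---|---|---|---|
| 6 months | 0.1 | 4.4% | 1.02 | 2.54 |
| 6 months | 0.2 | 8.6% | 1.05 | 2.48 |
| 6 months | 0.4 | 16.3% | 1.10 | 2.36 |
| 1 year | 0.1 | 7.7% | 1.05 | 2.48 |
| 1 year | 0.2 | 14.7% | 1.10 | 2.37 |
| 1 year | 0.4 | 27.0% | 1.21 | 2.15 |

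**Check against the protocol's comparator.** In an unrestricted pool, consenters stay in and may be transplanted faster after consenting. Assume their hazard becomes μ = 2.60λ = 1.160 per year, the ratio that 8.2 implies for MYTHIC. The share still waiting at t is S(t) = e^(−st) + g(e^(−st) − e^(−μt))/(μ − s), and the rate is (1 − S(F)) divided by the integral of S from 0 to F. Rates as multiples of λ, for g = 0.1, 0.2 and 0.4:
- 6 months: unrestricted 1.034, 1.067, 1.130; after exclusion 1.024, 1.050, 1.102.
- 1 year: unrestricted 1.058, 1.114, 1.217; after exclusion 1.048, 1.098, 1.208.
- 2 years: unrestricted 1.089, 1.171, 1.317; after exclusion 1.090, 1.188, 1.413.

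Against this comparator the exclusion slightly lowers the control rate at 6 months and 1 year. At 2 years the two are about equal at the lowest consent hazard, and exclusion gives the higher rate at the other two.

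**Limits.** The model averages a rate over follow-up. It does not reproduce the caliper matching or the stratified Cox fit.

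**The case against.** The SAP is a draft summary with a few bullets per analysis. Its silence on dates need not mean that later consent counts: the rule may be intended for consent status at sampling, in which case nothing is selected on later information. That stands as a statement about intent, but the text does not say so, and an analyst following it would drop anyone with a consent flag, whenever it was set.

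A reader might go further and infer that the control transplant rate is inflated outright. The documents do not support that. It requires both that later consent counts and that the target is waiting without access to viremic kidneys. Against the protocol's unrestricted pool the sign can reverse, as shown above.

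Other objections also stand. Where the overstatement occurs, it understates MYTHIC's advantage and so does not manufacture a benefit. The comparison is secondary, SVR12 is unaffected, and power has ample margin. Excluding candidates already open to viremic kidneys is a defensible contrast of access with no access, and the SAP does name its reduced pool. The 1:3 versus 1:5 difference is a separate inconsistency and is no evidence of bias. Finally, censoring at later consent may itself be informative, for example if candidates consent because they expect a long wait.

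**Conclusion.** The rule has no date and no time zero, and applied literally it selects controls, and the score used to match them, on future information. Relative to candidates without viremic access, this biases the hazard ratio toward the null: modestly over the protocol's estimated 6 months and more with longer follow-up, as tabulated. These sizes rest on assumed consent hazards, on consent being independent of transplant hazard, and on the 20% control figure in 8.2. If consent is fixed at time zero, this bias is absent. The change of comparator from the protocol is unreconciled whichever reading is intended. It should be corrected before the analysis is run, but it does not threaten the primary result.

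**What to change.** In Part 8(a) and 8(b):
- Set each control's time zero at the enrolment date of the matched MYTHIC participant.
- Exclude only candidates whose consent to a viremic kidney was recorded on or before that date, both when fitting the prognostic score and when matching.
- Censor a control at later consent, and add a sensitivity analysis that keeps such controls at risk, because the censoring may be informative.
- If the registry extract has no consent dates, report the comparison with and without the exclusion.
- State the comparator as candidates not open to viremic kidneys at time zero, and reconcile it and the matching ratio with the protocol (1:3 OPTN there, 1:5 SRTR* in the SAP).

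The cost is a few lines in a SAP still marked as a draft, a date condition in the registry extract and one extra model fit. No new trial data are needed. Whether the registry holds consent dates cannot be judged from the documents.
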